8.1. Statistical Methods

The planned statistical methods and analyses for the primary and all secondary endpoints are described in detail in Section 8.2.1 and Section 8.2.2 below.

To explore the data further and to assess the goodness-of-fit of all statistical models, separate SAS datasets will be provided by the clinical programmer to the statistician. Covariates for data exploration may include baseline and/or demographic covariates such as gender, age, weight (continuous and/or Pfizer standard categorical cut-offs), site, country, etc.

8.2. Statistical Analyses

Subject evaluation groups will show end of study subject disposition and will show which subjects were analyzed for safety (adverse events and laboratory data), pharmacokinetics (PK) and all secondary efficacy measures (FAS). Frequency counts will be supplied for subject discontinuation(s) by treatment. Data will be reported in accordance with the sponsor reporting standards.

A breakdown of demographic data will be provided for age, race, weight, body mass index, and height. Each will be summarized by treatment cohort in accordance with the sponsor reporting standards.

The following data will also be summarized by treatment and in accordance with the current sponsor reporting standards:

Discontinuations, adverse events, laboratory data, vital signs, ECG and concomitant medication data will be summarized by treatment and in accordance with current Pfizer data standards.

8.2.1. Safety Analysis

For all safety variables and vital signs, the baseline will be predose measurement taken either on the day of dosing or at the baseline or screening visit.

8.2.1.1. Adverse Events

All adverse event summaries will be presented for the complete study. Additionally, summary tables of the most frequent adverse events will be presented by cohorts. Based on the review of the frequency and timing of adverse events, additional summaries may be requested.

8.2.1.2. Vital Signs

Systolic blood pressure, diastolic blood pressure and pulse rate will be listed and tabulated by dose group and week with descriptive statistics. Change from baseline will also be summarized using the same descriptive statistics by dose group and visit.

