Weekly IV administration of PF-06252616, to juvenile cynomolgus monkeys (n=4/sex) for up to 26 weeks at doses of 0, 10, 50, or 284 mg/kg/week also resulted in hepatic iron accumulation at all doses, and adverse findings at 284 mg/kg/week affecting liver in both sexes and reproductive organs in females. The findings in the liver consisted of moderate to severe iron deposits in hepatocytes associated with portal macrophage accumulation and/or fibrosis, single cell necrosis and hepatocellular cytoplasmic rarefaction with correlating increases in alanine aminotransferase (ALT) and aspartate aminotransferase (AST) activities. Pigment deposit was also observed in the kidney, pancreas and duodenum of 1 female. Adverse findings in the female reproductive tract consisted of arrested development of ovarian follicles and atrophy of the endometrium, cervical mucosa, and vaginal epithelium. Following a 13-week recovery period (n=2/sex), adverse PF-06252616-related microscopic findings were still noted in the liver of male and female monkeys. In the liver, single cell necrosis and macrophage accumulation were present, and there was no reversal of the pigment deposit (iron/hemosiderin) and its associated changes. Pigment deposition was also present in the pancreas (including pancreatic lymph nodes) and kidney. Hepatic cytoplasmic rarefaction was not observed at the end of the recovery period suggesting a complete reversal of this change. In the female reproductive tract, some of the changes were still evident for 1 female while a complete recovery was noted for the other female.

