This study is primarily a safety and tolerability study of PF-06252616 in LGMD2I adults. The rationale for dose selection and escalation has been described above. A limited number of patients (4) will be enrolled in cohort 1 and will receive an initial dose of 5mg/kg PF-06252616 IV every 4 weeks. Following 16 weeks of treatment and a safety review, if no stopping rules have been met, 8 subjects will be enrolled in cohort 2 and receive 20mg/kg of PF-06252616. Subjects in cohort 2 will received 16 weeks of treatment and then a safety review will be performed. If no stopping rules have been met, cohort 1 will escalate to receive 40 mg/kg. This will occur after they have already received 5 mg/kg of PF-06252616 for 32 weeks. At the same time, cohort 3 will be enrolled and begin dosing at 40 mg/kg. For cohort 1, subject will receive 32 weeks of treatment with 5 mg/kg followed by an additionl 32 weeks of treatment with 40 mg/kg PF-06252616. The rationale for this design is that it provides a dose escalation to determine safety of each dose and allows each cohort to potentially receive a meaningful dose. Thirty-two weeks of treatment maximizes the opportunity to determine if there is a treatment effect at any given dose level. Finally, the design will provide long-term, 64 week dosing data on a limited number of subjects (4). All subjects, who completed the Follow-up period, will have the option to continue treatment in the extension period at 40mg/kg for up to 28 weeks in Cohort 1, up to 40 weeks in Cohort 2, and up to 24 weeks in Cohort 3

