**Cohort 1 (n=4):** 

- Lead-in period (16 weeks)
- Treatment A: PF-06252616 5 mg/kg (32 weeks)
- Treatment B: PF-06252616 40 mg/kg (32 weeks)
- Follow-up period (16 weeks)
- Extension period: PF-06252616 40 mg/kg (28 weeks)

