# 6.4. Active Treatment: Visit 4 (Day 29±3), 8 (Day 141±3), 10 (Day 197±3) and for Cohort 1, Visit 12 (Day 253±3), 16 (Day 365±3), 18 (Day 421±3)

- **Pregnancy Test**: A highly sensitive urine pregnancy test will be performed on all female subjects
- Diary Cards: For collection of first day of each menstrual cycle for WOCBP.
- Contraception Review: Confirmation of use of acceptable forms of contraception
- Weight
- Vital Signs: Supine blood pressure, pulse rate, respiratory rate, and oral temperature.
- Clinical laboratory testing:
  - Hematology with complete blood count and differential, comprehensive metabolic panel (sodium, potassium, chloride, carbon dioxide, blood urea nitrogen, creatinine, calcium, glucose, total protein, albumin, total bilirubin, AST, ALT, alkaline phosphatase) gamma-glutamyl transferase (GGT), prothrombin time (PT), activated partial thromboplastin time (aPTT), creatine kinase, amylase, cardiac troponin I. Urinalysis.
- Serum ferritin, serum iron, % transferrin saturation, TIBC: fasting blood collection
- Horomone Testing: LH, FSH, estrogen in WOCBP
- GLDH
- **Fecal Occult Blood:** Fecal sample is to be collected at home within 1 week prior to scheduled visit.
- C-SSRS

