# 6.8. Follow up: For Cohort 1, Visit 19 (Day 449±3) and for Cohort 2 and 3, Visit 11 (Day 225±3)

This visit will occur over 2 days.

- Physical Examination, including Nose and Throat Mucosal Exam.
- **Pregnancy Test**: A highly sensitive urine pregnancy test will be performed on all female subjects
- **Diary Cards:** For collection of first day of each menstrual cycle for WOCBP.
- Contraception Review: Confirmation of use of acceptable forms of contraception
- Weight
- Vital Signs: Supine blood pressure, pulse rate, respiratory rate, and oral temperature.
- 12-lead ECG: ECGs will be performed in triplicate
- Echocardiogram
- Clinical laboratory testing:

- Hematology with complete blood count and differential, comprehensive metabolic panel (sodium, potassium, chloride, carbon dioxide, blood urea nitrogen, creatinine, calcium, glucose, total protein, albumin, total bilirubin, AST, ALT, alkaline phosphatase) gamma-glutamyl transferase (GGT), prothrombin time (PT), activated partial thromboplastin time (aPTT), creatine kinase, amylase, cardiac troponin I. Urinalysis.
- Serum ferritin, serum iron, % transferrin saturation, TIBC: fasting blood collection
- Horomone Testing: LH, FSH, estrogen in WOCBP
- GLDH
- Fecal Occult Blood: Fecal sample is to be collected at home within 1 week prior to scheduled visit.
- C-SSRS
- **MRI-liver**: Liver MRI will be obtained for iron accumulation
- **MRI-muscle:** WB-MRI and dedicated thigh MRI will be performed for muscle quantity and quality
- **DXA Whole Body:** Whole body DXA will be performed for lean body mass assessment.
- **DXA Spine and Hip:** Spine and hip DXA will be performed for BMD.
- **Functional assessments:** Must be conducted in the following order: Respiratory function (FVC, FEV1, MIP, MEP), 4SC, 2MWT, 10-meter walk/run, TUG, strength assessment (MMT, hand-held dynamometry) and PUL.
- **Needle muscle biopsy:** Following WB-MRI and functional assessments, a needle muscle biopsy of the tibialis muscle will be performed.
- Quality of Life assessments
  - InQol
  - SF-36
- Immunogenicity sample collection.
- PD sample collection
- PK sample collection

- Adverse Event monitoring
- Infusion site reaction monitoring
- Concomitant medication

6.9. Follow-up: For Cohort 1, Visit 20 (Day 561±3) and for Cohort 2 and 3 Visit 12 (Day 337±3)

- Physical Examination, including Nose and Throat Mucosal Exam.
- **Pregnancy Test**: A highly sensitive urine pregnancy test will be performed on all female subjects

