2.1. Study Design

This is a Phase 1b/2, open-label multiple ascending dose study to evaluate the safety, tolerability, efficacy, PK and PD of PF-06252616 administered to in ambulatory participants diagnosed with LGM21. Three IV infused dose levels administered every 28 days will be investigated in a dose escalating fashion.

PF-06252616 dose levels:

- 5 mg/kg.
- 20 mg/kg.
- 40 mg/kg.

Approximately 20 eligible subjects will be consecutively assigned to 1 of 3 cohorts for approximately 96 weeks (cohort 1) or 64 weeks (cohorts 2 and 3).

Cohort 1 (n=4):

- Lead-in period (16 weeks)
- *Treatment A: PF-06252616 5 mg/kg (32 weeks)*
- Treatment B: PF-06252616 40 mg/kg (32 weeks)
- Follow-up period (16 weeks)

Cohort 2 (n=8):

- Lead-in period (16 weeks)
- Treatment: PF-06252616 20 mg/kg (32 weeks)
- Follow-up period (16 weeks)

Cohort 3 (n=8):

• Lead-in period (16 weeks)

[figure not shown]
- Treatment: PF-06252616 40 mg/kg (32 weeks)
- Follow-up period (16 weeks)

At each dose level, subjects will be followed for an initial 16-week lead-in period to establish individual change in disease progression.

The study will begin with 4 subjects being enrolled into Cohort 1. Following the lead-in period, subjects in Cohort 1 will be dosed with 5 mg/kg for a total of 32 weeks (8 doses). Cohort 2 will begin dosing at the mid dose level (20 mg/kg) once safety has been confirmed with subjects in Cohort 1 who have been treated for 16 weeks. Cohort 1 and 3 will begin dosing at the highest dose level (40 mg/kg) once safety has been confirmed with subjects in Cohort 2 who have been treated for 16 weeks.

Each dose level will be evaluated for 32 weeks (8 doses each). Cohort 1 is the only cohort who will receive 2 dose levels (5 mg/kg and 40 mg/kg) and their total treatment time will be 64 weeks.

At the conclusion of the treatment period, subjects will be followed for an additional 16 weeks to monitor for safety, PK and duration of response.

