6.1.2. Laboratory Data

Using the current Pfizer data standards, the last pre-dose value before the first day of dosing is used as the baseline for all laboratory parameters.

Clinical laboratory tests include hematology with complete blood count and differential, comprehensive metabolic panel (sodium, potassium, chloride, carbon dioxide, blood urea nitrogen, creatinine, calcium, glucose, total protein, albumin, total bilirubin, AST, ALT, alkaline phosphatase), cardiac troponin I, gamma-glutamyl transferase (GGT), prothrombin time (PT), activated partial thromboplastin time (aPTT), creatine kinase, amylase and urinalysis. If total bilirubin is abnormal, direct bilirubin will be tested reflexively. The samples for serum ferritin, serum iron, transferrin saturation and TIBC should be collected in the morning following an 8 hour fast. Hormone testing will include LH,FSH and estrogen in female subjects only. Laboratory monitoring will also be performed to detect ADA and NAb.

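### Cohort 1's 40 mg/kg period has no baseline of its own, and vital-sign changes by dose group and visit can put unlike exposures in the same row

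*SAP*

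**What the plan says.** SAP 2.1 states that "Cohort 1 is the only cohort who will receive 2 dose levels (5 mg/kg and 40 mg/kg"). Protocol 3.1 lists the first period as "Treatment A: PF-06252616 5 mg/kg (32 weeks"), and Protocol 6.3 puts the first 40 mg/kg dose at Visit 11, Day 225. The design rationale (Protocol 1.11) is that "it provides a dose escalation to determine safety of each dose".

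Baselines are set in several places:

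- **Laboratory data (SAP 6.1.2):** "the last pre-dose value before the first day of dosing is used as the baseline for all laboratory parameters".
- **ECG (Protocol 9.3.2):** the averaged predose triplicate at Week 0. Protocol 7.1.4 likewise uses Day 1 for QTc.
- **Vital signs, ECG and echocardiogram (SAP 6.1.1) and all safety variables (SAP 8.2.1):** a predose value on the day of dosing, or at the baseline or screening visit. Neither section says the first day of dosing.

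No section gives a second baseline for Cohort 1.

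Tabulation also varies. Vital-sign values are by dose group and week, while for changes SAP 8.2.1.2 says "Change from baseline will also be summarized using the same descriptive statistics by dose group and visit". QTcF categories are by treatment and visit, and ECG changes by treatment and study week (SAP 8.2.1.3). The planned vital-sign figures in SAP Appendix 1 are by dose level, without cohort. The safety sections do not define dose group. The efficacy model in SAP 8.2.2 has a separate 5 + 40 mg/kg category.

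**The concern.** The primary objective is the safety of each ascending dose, and Cohort 1 contributes to two of them. With a baseline taken before any drug, its change at 40 mg/kg is the sum of what happened over 32 weeks at 5 mg/kg and what happened afterwards. Cohort 3's change at 40 mg/kg has only the second part. The gap can be longer than planned, because Protocol 3.5 allows a break of open length between the two doses.

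Persistence is plausible for at least one measure. In the 26-week monkey study, after 13 weeks of recovery, "there was no reversal of the pigment deposit (iron/hemosiderin) and its associated changes" (Protocol 1.7).

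The second issue is alignment. After Visit 10 the same visit number means different things in the two cohorts that receive 40 mg/kg. The heading of Protocol 6.4 has "for Cohort 1, Visit 12 (Day 253±3), 16 (Day 365±3), 18 (Day 421±3") as dosing visits, while the heading of Protocol 6.9 has "for Cohort 2 and 3 Visit 12 (Day 337±3") as off-drug follow-up. A 40 mg/kg row built on visit number can average subjects on treatment with subjects long off it.

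**Working it through.** The documents give no figure to reproduce here, so the check is schedule arithmetic. It covers the main study only, as the SAP does. In the protocol's extension, Cohorts 2 and 3 also receive 40 mg/kg at visits numbered from 13.

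**Inputs.** Cohort 1 n=4 and Cohort 3 n=8 (Protocol 3.1). Dosing is every 28 days, 8 doses per level. Dosing days are in Protocol Section 5 and visit days in the Schedule of Activities. The half-life in healthy adults is about 12 to 19 days (Protocol 1.8).

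**Start of 40 mg/kg in Cohort 1.** 8 × 28 = 224 days = 32 weeks, so the first 40 mg/kg dose is on Day 225, Visit 11. This agrees with the protocol.

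**Shared rows, if dose group means dose level:**

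| Row | Cohort 1 (n=4) | Cohort 3 (n=8) |
|---|---|---|
| Visit 11 | Day 225, before or at first 40 mg/kg dose | Day 225, 225 − 197 = 28 days after eighth dose |
| Visit 12 | Day 253, 253 − 225 = 28 days after first 40 mg/kg dose | Day 337, 337 − 197 = 140 days after last dose |

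At Visit 12, Cohort 3 is 140/19 = 7.4 to 140/12 = 11.7 half-lives past its last dose. In the main study, 40 mg/kg rows for Visits 3 to 10 hold only Cohort 3, and those for Visits 13 to 20 hold only Cohort 1.

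**Study week instead of visit.** This does not repair the alignment. Day 225 is still shared. Day 337 is Visit 15 in Cohort 1, after four 40 mg/kg doses, and off-drug Visit 12 in Cohort 3.

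**ECG.** Cohort 1 has ECGs at Visits 11, 14, 19 and 20 from Day 225 on. Cohort 3 has them at Visits 3, 6, 11 and 12. Only Visit 11 is shared, and the Cohort 1 tracing there precedes any 40 mg/kg dose (Protocol 6.3).

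**Effect of the baseline.** Let d5 be the mean change over the 5 mg/kg period, assumed to persist, and d40 the change due to 40 mg/kg, taken as equal in both cohorts.

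- From a pre-drug baseline, Cohort 1 at 40 mg/kg shows d5 + d40.
- From the Visit 11 predose value, it shows d40.
- A summary pooling both cohorts at equal time on 40 mg/kg would show (4(d5 + d40) + 8 d40)/12 = d40 + d5/3.

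The by-visit rule does not produce that last summary. The point 28 days after the eighth 40 mg/kg dose is Visit 19 in Cohort 1 (449 − 421 = 28) and Visit 11 in Cohort 3, which are different rows.

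**Residual drug at Visit 11** (one compartment, no break in dosing). With r = 2^(−28/h), the share of exposure in the first 40 mg/kg interval that comes from earlier 5 mg/kg doses is 5r(1 − r^8) / [5r(1 − r^8) + 40(1 − r)]. For h = 12, r = 0.198 and the share is 3%. For h = 19, r = 0.360 and the share is 7%.

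**The case against.** The strongest reply is that the gap is narrow.

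- **Scope.** A reader might infer that safety as a whole is pooled by dose and visit. The documents do not support that: the rule in SAP 8.2.1.2 covers vital-sign changes. Most planned adverse-event tables and the laboratory abnormality table show cohort, and the latter disregards baseline. LVEF shift tables are by cohort and total. This stands.
- **Liver iron.** A reader might infer that carried-over liver iron is charged to 40 mg/kg in a pooled table. R2* change is tabulated per subject (SAP 8.2.1.5), and the planned summary is by visit and magnet field strength, not dose. Accrual at 5 mg/kg is also conjectural, since Protocol Table 1 gives a 28.7-fold average-concentration margin at that dose. This stands too.
- **Residual antibody.** At 3% to 7% of first-interval exposure it is minor. The issue is persisting change and elapsed time, which this figure does not address.
- **Meaning of dose group.** If safety tables adopt the 5 + 40 mg/kg category of SAP 8.2.2, Cohorts 1 and 3 are not pooled. That is fair, but the safety sections do not say so, and the dose-level figures point the other way.
- **Choice of baseline.** For cumulative toxicity, change from before any drug is a defensible measure, and a Visit 11 baseline would subtract earlier accumulation. This is a good reason to keep the pre-drug baseline and add the second display beside it.
- **Consequence.** The analyses are descriptive, listings cover every subject, and escalation rests on safety committee review. That limits the harm, but the dose-specific summaries still need a clear meaning.

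**Conclusion.** The concern holds in limited form. No baseline exists for Cohort 1's 40 mg/kg period. Its laboratory and ECG changes at 40 mg/kg therefore include any change during 32 weeks at 5 mg/kg, and showing cohort separately does not remove that. The vital-sign and general safety baseline can be read as Day 1 or Day 225. Day 1 is the more natural reading, but the text does not settle it.

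If dose group means dose level, vital-sign changes mix unlike exposures in two main-study rows, Visits 11 and 12, and QTcF categories do so at Visit 11 only. The subjects concerned are 4 of the 12 who receive 40 mg/kg in the main study.

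No bias size can be stated, because the documents give no estimate of change at 5 mg/kg. A reader might infer that pooled 40 mg/kg results are overstated by d5/3. That would apply only to a summary pooling both cohorts at equal time on 40 mg/kg, which the by-visit rule does not create.

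**What to change.** In SAP 6.1 and 8.2.1:

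1. State that the overall baseline is the last value before the first dose of study drug, and keep it for cumulative change.
2. Add a second display for Cohort 1's 40 mg/kg period, using the Visit 11 predose value as baseline. Vital signs, weight, ECG, laboratory tests, iron indices, liver MRI and DXA are already scheduled there.
3. Define dose group so that Cohort 1 at 40 mg/kg is its own column, labelled 5 + 40 mg/kg as in SAP 8.2.2.
4. Index by-dose safety tables and figures by weeks since first dose at that level, with follow-up in separate rows by weeks since last dose. This also copes with a break between doses.
5. State that LVEF and LVESV change in Cohort 1 cannot be split by dose, because no echocardiogram is scheduled between screening and Visit 19.

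The cost is SAP wording, programming and a few extra displays. No new data are needed.

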8.2.1.3. Electrocardiogram

The following ECG data will be listed: QT, QTc (Fridericia's), heart rate, QRS duration, PR and RR interval.

Baseline and change from baseline for QT, QTcF, heart rate, QRS, PR and RR will be summarized using descriptive statistics by treatment and study week. Any triplicate measurements will be averaged prior to the calculation of summary statistics. For QTcF a classification of absolute values and increase from baseline will be used.

The number of subjects with average of the triplicate QTcF < 450 ms, $450 \text{ ms} \leq QTcF < 480 \text{ ms}$, $480 \text{ ms} \leq QTcF < 500 \text{ ms}$ and QTcF values $\geq 500 \text{ ms}$ will be tabulated by treatment and visit. The number of subjects with maximum increase from baseline QTcF < 30 ms, $30 \text{ ms} \leq QTcF < 60 \text{ ms}$ and $QTcF \geq 60 \text{ ms}$ will be tabulated by treatment and study week. In addition, the number of subjects with uncorrected QT values $\geq 500 \text{ ms}$ will be summarized.

Triplicate measures will be averaged prior to categorizing subjects. However, the number of subjects with any single uncorrected QT value \geq 500 ms (not the average) will be *summarized.*

8.2.1.4. Cardiac MRI/Echocardiogram

The mean absolute and percent change from baseline in LVEF and LVESV will be evaluated. LVEF shift tables will be prepared for cohorts and the total.

8.2.1.5. Liver MRI

The mean absolute and percent change from baseline in the R2* value will be tabulated for *each subject*. Summaries of the categorical assessment of iron overload (normal, above normal, etc.) will be presented.

8.2.1.6. Other Safety Data

C-SSRs, DXA (spine and hip), prior medication(s), medical history and physical examination will be listed in accordance with the sponsor reporting standards but not subjected to formal statistical analysis.

Any other screening data that is captured on the study database will be listed.

8.2.1.7. Immunogenicity

Immunogenicity analysis will be based on the immunogenicity analysis population which will be the same as the safety analysis population. This will include anti-drug antibody and neutralizing antibody development by all visits with ADA samples until the end of follow-up. Both continuous endpoints (titer) and categorical endpoints (i.e. positive, negative and inconclusive) will be reported for the anti-drug antibody and neutralizing antibody assays by dose and sampling time points. Data permitting, the incidence of anti-drug antibody and neutralizing antibody will be summarized by time points within each dose cohort and may be also summarized by dose. The impact of anti-drug antibody and neutralizing antibody on PK and PD parameters and profiles, efficacy and safety may be also evaluated but no formal statistical inference will be drawn.

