#### 1.9.2. Immunogenicity Results B5161001

Following PF-06252616 administration in Study B5161001, 5 adult healthy subjects in the single dose groups (1 in the 1 mg/kg IV group, 2 in the 20 mg/kg IV group, and 2 in the 3 mg/kg SC group) and 1 subject in the 10 mg/kg IV repeat dose group were found to have treatment-induced ADA responses. Among the 6 subjects with ADAs, 4 subjects (1 in each of the 1 mg/kg IV, 3 mg/kg SC, 20 mg/kg IV, and 10 mg/kg repeat dose IV cohorts) have shown neutralizing antibodies (NAb). However, none of these subjects with NAb showed any discernibly lower GDF-8 levels than others in the same cohort. In summary, for Study B5161001, there was a confirmed ADA incidence rate of 11.3% but without any obvious impact on the PF-06252616 PK or GDF-8 modulation. None of these subjects experienced clinical signs or symptoms consistent with an immune response.

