#### 6.15. Subject Withdrawal

Subjects who request to discontinue study treatment will remain in the study and must continue to be followed for protocol specified follow-up procedures. The only exception to this is when a subject specifically withdraws consent for any further contact with him/her. The subject should notify the investigator of the decision to withdraw consent from future follow-up in writing, whenever possible. The withdrawal of consent should be explained in detail in the medical records by the investigator, as to whether the withdrawal is from further treatment with study drug only or also from study procedures and/or post treatment study follow-up, and entered on the appropriate CRF page. In the event that vital status (whether the subject is alive or dead) is being measured, publicly available information should be used to determine vital status only as appropriately directed in accordance with local law.

If the subject withdraws from the study and also withdraws consent for disclosure of future information, no further evaluations should be performed and no additional data should be collected. The sponsor may retain and continue to use any data collected before such withdrawal of consent.

Subjects may withdraw from the study at any time at their own request, or they may be withdrawn at any time at the discretion of the investigator or sponsor for safety or behavioral reasons, or the inability of the subject to comply with the protocol-required schedule of study visits or procedures at a given study site.

If a subject does not return for a scheduled visit, every effort should be made to contact the subject. All attempts to contact the subject and information received during contact attempts must be documented in the subject's medical record. In any circumstance, every effort should be made to document subject outcome, if possible. The investigator should inquire about the reason for withdrawal, request that the subject return for a final visit, if applicable, and follow-up with the subject regarding any unresolved AEs.

It may be appropriate for the subject to return to the clinic for final safety assessments and to be questioned regarding their reason for withdrawal. The following assessments may be performed according to the Schedule of Activities:

Assessments in the Early Withdrawal visit may include:

- Physical Examination, including Nose and Throat Mucosal Exam.

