# 7.4. Anti-Drug Antibody (ADA) anti-PF-06252616 and Neutralizing Antibody (NAb)

During all study periods, blood samples (2 mL) to provide serum for analysis of anti-PF-06252616 will be collected into the appropriate tubes (containing no anticoagulant or gel separator) at times specified in the Schedule of Activities section of the protocol.

All efforts will be made to obtain the samples at the exact nominal time relative as described in the Schedule of Activities.

Samples will be analyzed using validated analytical methods in compliance with Pfizer standard operating procedures. All samples that are positive in a screening assay will be confirmed for antibody specificity and further characterized for titer. Samples that are determined to be positive for ADA may be further tested for the presence of neutralizing antibodies.

The PK and immunogenicity samples must be processed and shipped as indicated to maintain sample integrity. Any deviations from the PK processing steps, including any actions taken, must be documented and reported to the sponsor. On a case-by-case basis, the sponsor may make a determination as to whether sample integrity has been compromised. Any sample deemed outside of established stability, or of questionable integrity, will be considered a protocol deviation.

As part of understanding the pharmacokinetics or immunogenicity of the study drug, samples may be used for further characterization and/or evaluation of the bioanalytical method. These data will be used for internal exploratory purposes and will not be included in the clinical report. Samples collected for this purpose will be retained in accordance to local regulations and if not used within this timeframe, will be destroyed.

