5. ANALYSIS SETS

5.1. Full Analysis Set

All analyses will be based on the full analysis set (FAS) which includes all enrolled subjects who have received at least one dose of study drug.

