5.2. Safety Analysis Set

Safety analyses will be based on the full analysis set.

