5.3. Other Analysis Sets

5.3.1. PK Concentration Analysis Set

The PK concentration population is defined as all enrolled subjects who received at least 1 dose of PF-06252616 and in whom at least 1 concentration value is reported.

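### ADA and NAb incidence is set on all dosed subjects and summarised by time point, with no rule tying it to the pre-dose result or to having a post-dose sample

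*SAP*

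**What the plan says.** **Population.** SAP 8.2.1.7 states: "Immunogenicity analysis will be based on the immunogenicity analysis population which will be the same as the safety analysis population". SAP 5.2 adds: "Safety analyses will be based on the full analysis set". SAP 5.1 describes that set as one "which includes all enrolled subjects who have received at least one dose of study drug". No antibody result is required. Appendix 1 of the SAP also puts the ADA status table (14.1.1.62, by dose level) on the full analysis set. By contrast, SAP 5.3.1 limits the PK set to dosed subjects "in whom at least 1 concentration value is reported", and SAP 5.3.2 has the same condition for GDF-8.

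**Endpoint and summary.** The endpoint in SAP 4.2.2.5 and Protocol 2.2.2.4 is the incidence of ADA and NAb *development*. SAP 8.2.1.7 reports titre and a three-way status (positive, negative, inconclusive) by dose and sampling time. Where data allow, it summarises incidence by time point within cohort. It does not define development, treatment-induced or boosted ADA, or the percentage denominator. SAP 6.1 asks for ADA and NAb incidence by day 1 (meant to describe low-dose safety) and day 561 in Cohort 1, and by day 337 in Cohorts 2 and 3.

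**Sampling.** The Schedules of Activities mark immunogenicity at Visit 3 (Day 1) and Visit 11 (Day 225). After that it is marked at Visits 19 and 20 (Days 449 and 561) in Cohort 1, at Visit 12 (Day 337) in Cohorts 2 and 3, and at early withdrawal. Protocol 6.3 lists the Visit 3 sample among the pre-dose procedures. For early withdrawal, Protocol 6.15 says: "The following assessments may be performed according to the Schedule of Activities". For NAb, Protocol 7.4 says: "Samples that are determined to be positive for ADA may be further tested for the presence of neutralizing antibodies".

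**The concern.** Two kinds of subject are not provided for. One is dosed, leaves before Day 225 and gives no further sample. That subject cannot be found positive but belongs to the stated population. The other is already ADA-positive at Visit 3. A display of status by time point shows that subject as positive at later visits too, and nothing says whether this is development.

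The day 1 cut-off raises the same issue more sharply. In Cohort 1 it asks for low-dose incidence at a time when the only sample precedes the first dose.

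Immunogenicity is a named secondary objective, the cohorts hold 4, 8 and 8 subjects, and only a few cases can be expected. The rule for one subject can therefore visibly change a reported rate, so it should be fixed before results are read.

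**Working it through.** **1. The earlier rate, reproduced.** Protocol 1.9.2 reports that 5 single-dose subjects and 1 repeat-dose subject "were found to have treatment-induced ADA responses", and gives an incidence of 11.3%. Protocol 1.12 gives 42 + 11 = 53 subjects who received the drug.
- 6/53 = 11.3%. Neighbouring denominators do not fit (6/52 = 11.5%, 6/54 = 11.1%), nor do all 73 enrolled (6/73 = 8.2%).
- The earlier figure is therefore treatment-induced ADA over all dosed subjects.
- At that rate, 20 × 6/53 = 2.3 cases would be expected here.

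**2. Inputs for this trial.** SAP 2.1: "Approximately 20 eligible subjects will be consecutively assigned to 1 of 3 cohorts", with n = 4, 8 and 8. The documents do not predict the number without a post-dose sample (m) or the number positive only because they were positive at Visit 3 (b). Both are assumed ranges. Let t be the number of treatment-induced cases and N the number dosed.

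**3. Denominator.** Compare t/N (all dosed) with t/(N − m) (those with a post-dose result).

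| N | t | m | t/N | t/(N − m) | difference |
|---|---|---|---|---|---|
| 20 | 2 | 1 | 10.0% | 2/19 = 10.5% | 0.5 points |
| 20 | 2 | 2 | 10.0% | 2/18 = 11.1% | 1.1 points |
| 20 | 2 | 3 | 10.0% | 2/17 = 11.8% | 1.8 points |
| 8 | 1 | 1 | 12.5% | 1/7 = 14.3% | 1.8 points |
| 4 | 1 | 1 | 25.0% | 1/3 = 33.3% | 8.3 points |

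With m = 0 the two rates are equal.

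**4. Numerator.** If Visit 3 positives are counted, the rate is (t + b)/N instead of t/N, a difference of b/N. For b = 1 this is 1/20 = 5 points overall, 1/8 = 12.5 points in Cohort 2 or 3, and 1/4 = 25 points in Cohort 1. With t = 2 and N = 20, b = 1, 2, 3 gives 15%, 20%, 25% against 10%. With b = 0 there is no difference.

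**5. Both together.** With t = 2, b = 1 and m = 2, the rate is 3/20 = 15.0% against 2/18 = 11.1%. The two effects run in opposite directions and partly cancel.

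**6. Day 1 in Cohort 1.** SAP 6.1 asks for incidence by day 1. The Day 1 sample is pre-dose (Protocol 6.3), so a positive by that date can only be pre-existing. The first scheduled sample after 5 mg/kg dosing is Visit 11, nominally Day 225, taken after eight doses and before the first 40 mg/kg dose. Protocol 6.3 covers Visit 3 and Cohort 1 Visit 11 in one list and labels the sample as baseline. Without a rule, an antibody that arose on 5 mg/kg could be read as baseline for 40 mg/kg.

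**The case against.** The strongest reply is that the SAP leaves rules open and does not state wrong ones. Much of it stands, and it rules out several stronger readings.

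- *That the SAP counts any positive.* A reader might infer this from the three-way status. The text says development and gives no counting rule. Visit 3 is itself a sampling time, so a pre-existing positive and its titre would be visible. The defect is a missing definition.
- *That incidence is wrong in both directions.* Either effect needs a subject of the relevant kind. Percentages by time point may be taken over those sampled; the SAP does not say.
- *That untested positives count as NAb-free.* Testing is optional, but no passage says how untested samples are classified.
- *That the denominator makes the rate incomparable with 11.3%.* Step 1 shows that the earlier rate also uses all dosed subjects, and no comparison is planned. Only a different numerator definition could break comparability.
- *That the change exceeds any plausible dose difference.* No figure in the documents supports this.

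Further points also stand. Protocol 6.15 keeps subjects who stop treatment in follow-up, and the schedules mark an antibody sample at early withdrawal, so unsampled subjects would mainly be those who withdraw consent or are lost. The PK and GDF-8 sets do not require a post-dose value, so the same rule for ADA would normally exclude nobody, because a Visit 3 sample is scheduled for all. SAP 6.1 refers to sponsor data standards, which may hold definitions that the documents do not show.

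The reply does not remove three facts: the population is a stated rule with no result required, nothing ties incidence to the Visit 3 result, and the day 1 cut-off cannot deliver what SAP 6.1 wants from it.

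**Conclusion.** The point holds conditionally. An all-dosed denominator understates incidence if some subjects have no post-dose sample. The effect is small overall and larger within a cohort. Status by time point can overstate development if some subjects are positive at Visit 3, and that effect is larger per subject. The sizes in steps 3 to 5 rest on assumed counts and on the planned cohort sizes. The day 1 problem needs no such assumption.

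The endpoint is secondary and descriptive. SAP 8.2.1.7 plans no formal inference on the impact of antibodies, and Protocol 9.1 reports no sample size calculation. Severity is minor to moderate.

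**What to change.** Amend SAP 8.2.1.7, SAP 6.1 and the shell of Table 14.1.1.62:

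- Base ADA incidence on dosed subjects with at least one post-dose ADA result. Show the number evaluable, and give the all-dosed rate alongside, which keeps the denominator of the earlier study. State how inconclusive results are handled.
- Count as treatment-induced a subject negative at Visit 3 and positive at any post-dose sample. Show Visit 3 positives separately, with any rise in titre.
- Make Visit 3 the only ADA baseline, so that the Cohort 1 Visit 11 sample counts as post-dose for 5 mg/kg.
- Report NAb results with the number of ADA-positive subjects tested.
- In SAP 6.1, replace the day 1 cut-off for Cohort 1 with the Visit 11 pre-dose sample.

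The cost is SAP wording and one table shell, with no new samples. The drawback is that the evaluable denominator may be slightly smaller than the safety set.
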